1. OBJECTIVES

1.1 Study Design

This is a prospective, randomized, double-blind, signal detection trial comparing placebo gel plus best practice standards (BPS) with topical tazarotene 0.1% gel plus BPS for the prevention of grade-2 or greater HFSR in patients treated with regorafenib monotherapy. BPS is defined as 20% urea cream + DFCI approved teaching sheets + pharmacy call for oral chemotherapy teaching.

1.2 Primary Objectives

To test the hypothesis that the preventative use of 0.1% tazarotene gel daily in addition to BPS (20% urea cream daily, with pharmacy call and DFCI approved teaching sheets) reduces the development of grade-2 or greater hand-foot skin reaction (HFSR) compared with placebo gel plus BPS.

1.3 Secondary Objectives

- (1) To test the hypothesis that the preventative use of 0.1% tazarotene gel daily in addition to BPS:
 - a. Decreases regorafenib dose modification due to HFSR
 - b. Improves health-related quality of life associated with HFSR as assessed by skindex-16 survey, dermatology quality life index (DLQI) and hand-foot syndrome 14-item scale (HFS-14) prior to initiating the TKI, then at 2-4 week intervals depending on the tool
 - c. Decreases global stress associated with HFSR as measured prior to initiating the TKI, then at 4 week intervals using the 10-item perceived stress scale (PSS), which has been validated in both healthy people and cancer patients.

2. BACKGROUND

2.1 Study Disease(s)

Tyrosine kinase inhibitors (TKI) are approved for the management of broad-reaching cancers that include colorectal cancer, renal cell carcinoma, gastrointestinal stromal tumors (GIST), pancreatic neuroendocrine tumor, thyroid and liver malignancies. Such targeted therapies are associated with different adverse events than their cytotoxic predecessors, with a greater frequency of side effects in the skin.

The most frequent toxicities with TKIs are dermatologic, particularly hand-foot skin reaction (HFSR) occurring in all grades in 40-85% of patients on regorafenib¹, 34% of patients on sorafenib² and 19% of patients on sunitinib³; grade 3 HFSR is reported at 13-33%¹, 9%² and 6%³ for each of the drugs respectively. The incidence of HFSR of any grade from regorafenib is highest in renal cell carcinoma (71.4%) followed by GIST (60.2%), hepatocellular carcinoma (50%) and metastatic colorectal carcinoma (46.6%).⁴ Grade-3 toxicity from HFSR is defined by severe skin changes that are painful and may include blisters, bleeding, edema and hyperkeratosis.⁵ Grade-3 toxicities limit self-care activities of daily living (ADLs). Importantly, grade-2 HFSR, a more common event, is also associated with pain, and limits instrumental ADLs. HFSR is one of the most, if not the most, common reason for dose reduction, interruption or discontinuation of regorafenib therapy.^{6,7,8,9}

HFSR has been shown to negatively impact health-related quality of life (HRQOL), more severely with higher-grade disease, as measured using the skindex-16 score, which incorporates symptom, emotion and function domains.¹⁰

Importantly, in the absence of evidence from prospective trials on the prevention of this toxicity, the current recommendation for patients with grade-3 toxicity is to hold the drug until severity declines. When the dose is restarted, it is done so at a lower level. With grade-2 toxicity, dose reduction is considered first line.

Recommendations for supportive care are varied and based primarily on expert opinion or consensus from historical experience with similar eruptions. In the oncology literature, the focus tends to be on how best to reduce doses and reinstitute the TKI.

Given the number of malignancies treated with TKIs, the increasing numbers of TKIs in trials, the long-term duration of therapy required, the frequency of HFSR with these medications, the impact on dose and therefore potential outcomes and the impact on patient quality of life, prospectively evaluated preventative measures are imperative such that evidence based, patient-centered guidelines can be developed. Given that regorafenib has highest rates of HFSR, the drug's dose-limiting toxicity, this study aims to provide an evidenced-based approach to preventing or reducing severity of HFSR.

2.2 IND Agent

Tazarotene 0.1% gel is a topical retinoid that was FDA approved in 1997 for the treatment of psoriasis and acne. It is converted via rapid de-esterification to its active form ("tazarotenic acid") in humans, which binds to retinoic acid receptors (RAR). While relatively selective for RAR β , it binds all three RAR, including RAR α and RAR γ . In psoriasis models, tazarotene blocks epidermal proliferation as well as inflammation. This class of topical medications is thought to be overall anti-hyperproliferative and to normalize differentiation of keratinocytes.

2.3 Rationale

There are no clinical or molecular risk factors that have been shown to predict those patients who are predisposed to the development of HFSR. The addition of friction/trauma and heat seems to play a role. Current treatment of HFSR is based on avoiding triggers and treating hyperkeratosis with urea-based products. Urea is a keratolytic and is thought to soften and breakdown thickened skin. There are no studies or trials published to date that attempt to address the underlying pathophysiology of HFSR, rather studies to date have only tried to suppress the clinical features and symptoms.

While, the pathophysiology of HFSR is still being elucidated, there have been a multitude of studies proposing several mechanisms. Some preclinical evidence suggests that there is dysregulation in keratinocyte differentiation, leading to hyperkeratosis, pain and inflammation in the setting of tyrosine kinase inhibition. This clinically and histologically resembles palmoplantar psoriasis in many cases. These findings are supported by the histopathology of HFSR as demonstrated by acanthosis, papillomatosis, hyperkeratosis and necrosis.¹¹ More recently, direct keratinocyte toxicity via anion transporter, OAT6, has been implicated in HFSR in the setting of sorafenib use.¹² Additionally, several studies have implicated the inhibition of anti-angiogenic receptors such as PDGFR and VEGFR in the etiology of HFSR.¹³

Retinoids are vitamin A derivatives that act on the nuclear receptors RAR and/or RXR. These receptors are highly expressed in keratinocytes and control a variety of cellular differentiation functions. Topical tazarotene gel is FDA approved for use in psoriasis, a hyperproliferative cutaneous disorder. Psoriasis shares many clinical and histopathological features with HFSR and both are caused by keratinocyte dysregulation. Tazarotene has been shown to have anti-inflammatory properties and normalize keratinocyte differentiation. Most recently, the RAR receptor blockade, specifically with tazarotene, has been shown to locally promote angiogenesis and may address the anti-angiogenic physiology of HFSR.¹⁴ In our experience, patients with established HFSR have responded to both topical and oral retinoids with marked improvement in symptoms.

By pre-emptively normalizing keratinocyte differentiation, decreasing inflammation associated with keratinocyte toxicity and locally promoting angiogenesis, we propose that topical retinoids, in addition to best practice standards, will diminish the incidence of HFSR, decrease dose modifications due to HFSR, decrease impact on patient quality of life and decrease global stress in those treated with regorafenib. To address our objectives, we propose a randomized signal detection trial to assess the preventative effectiveness of tazarotene plus best practices standards (BPS) compared with BPS alone.

2.4 Correlative Studies Background

- The primary goal of the correlative science is to begin to understand the pathways involved in the development of HFSR and, ideally, those pathways that are disrupted by our interventions
- Day 1 and 4 week (+/- 2 weeks) skin biopsies will be obtained from a cohort of 12 patients. Pre-biopsies will be taken from the lateral palm. On study biopsies will be taken from the same area in unaffected patients and from diseased areas in affected patients.
- A 4mm punch biopsy will be obtained from 12 patients (6 in each study arm); we suspect that half of patients in the control arm will develop HFSR on regorafenib and half will not. This will allow for comparison across arms and between affected and non-affected individuals to look for a signal of difference.
- Biopsies will be analyzed using standard immunohistochemistry and cyclic immunofluorescence, for the presence of activation of transcription factors known to be associated with hyper-proliferative inflammatory acquired and genetic skin disorders. Additionally, RNA transcriptional profiling will be performed to compare those patients who develop HFSR from those who do not using the nanostring platform on formalin-fixed, paraffin embedded tissue.

3. PARTICIPANT SELECTION

3.1 Eligibility Criteria

3.1.1

Participants must have histologically or cytologically confirmed solid tumors with a plan to initiate regorafenib, or having started regorafenib in the last 96 hours, via dose escalation protocol describe in the ReDOS study in CRC. The ReDOS study recommends this dose escalation of regorafenib: 80mg daily x 1 week, 120mg daily x 1 week, 160mg daily times one week, off week, then 160mg daily goal, or maximum tolerated dose thereafter. This is not a separate study; this is the current standard of care for regorafenib dosing. In addition, to compare

across the cohorts, patients must be ambulatory with full use of all 4 distal extremities.

- 3.1.2 Age ≥ 18
- 3.1.3 ECOG performance status ≤ 2 (Karnofsky $\geq 60\%$, see Appendix A)
- 3.1.4 Participants must have sufficient organ and marrow function in the opinion of the treating investigator. This can be based on lab reports from an outside facility.
- 3.1.5 Women of child-bearing potential (WOCBP) and men must agree to use adequate contraception (hormonal or barrier method of birth control; abstinence) prior to study entry and for the duration of study participation
Tazarotene is known to be teratogenic, although the dose required with topical application to affect the developing human fetus is unknown. Should a woman become pregnant or suspect she is pregnant while she or her partner is participating in this study, she should inform her treating physician immediately. Men treated or enrolled on this protocol must also agree to use adequate contraception prior to the study, for the duration of study participation, and 4 months after completion of administration.
- 3.1.6 Women of child-bearing potential (WOCBP) must have a negative serum pregnancy test.
- 3.1.7 Ability to understand and the willingness to sign a written informed consent document.

3.2 Exclusion Criteria

- 3.2.1 Known hypersensitivity to tazarotene
- 3.2.2 Regorafenib use in combination with another TKI (unless regorafenib was started in the last 96 hours.)
- 3.2.3 Pregnancy or non-compliance with contraception (4 weeks before, during and for at least 3 ovulatory cycles after treatment cessation). Pregnant women are excluded from this study because tazarotene is category X with the potential for teratogenic or abortifacient effects.
- 3.2.4 Nursing or lactating: Because there is an unknown but potential risk for adverse events in nursing infants secondary to treatment of the mother with tazarotene, breastfeeding should be discontinued if the mother is treated.
- 3.2.5 A history of hypervitaminosis A
- 3.2.6 Other systemic retinoids needed for another condition (ie. Isotretinoin for inflammatory acne, acitretin for psoriasis, bexarotene for CTCL).
- 3.2.7 Need for treatment dose systemic steroids or systemic immunosuppressive agents (i.e., for autoimmune disease or cerebral edema) at the time of enrolment
- 3.2.8 Psoriasis or other autoimmune disease requiring skin directed or systemic therapy known to impact keratinocyte proliferation (UV therapy to the hands or feet, TNF inhibitors, etc).

- 3.2.9 Active skin disease of the hands or feet with redness, scaling or blisters prior to enrolment
- 3.2.10 Participants who have had any systemic chemotherapy or immunotherapy within 4 weeks prior to entering the study AND who have not recovered from adverse events on the hands and feet due to the agents administered.
- 3.2.11 Participants who are receiving any other investigational agents to treat HFSR.
- 3.2.12 Uncontrolled intercurrent illness including, but not limited to, uncontrolled lower extremity edema, ongoing or active infection, symptomatic congestive heart failure, unstable angina pectoris, cardiac arrhythmia, or psychiatric illness/social situations that would limit compliance with study requirements.

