5. TREATMENT PLAN

This is a prospective, randomized, double-blind signal detection trial comparing placebo gel plus BPS (20% urea + DFCI approved teaching sheets + pharmacy call) to tazarotene 0.1% gel plus BPS for the prevention of HFSR in patients treated with regorafenib. Each study cycle is 28 days long.

At the time of consent for regorafenib, patients will be invited to participate, consented and enrolled. Patients may already have had their first dose of regorafenib before consenting to this study, as long as regorafenib was started less than 96 hours from first application of tazarotene. Patients will be randomized 1:1 to receive either placebo gel plus best practice standards (BPS) or BPS plus tazarotene 0.1% gel daily. The current standard of care for Regorafenib includes providing patients with oral chemotherapy teaching sheets that include a Hand Skin Foot Reaction teaching sheet, pharmacy instruction and 20% urea cream daily. Participants in both arms will have urea recommended as standard best practice standards. It is available over the counter and will not be supplied.

Patients will receive regorafenib for their malignancy per their treating medical oncology team. Regorafenib is not provided as part of this study. The study team will not be making any recommendations for dose, timing of dose, concomitant medications associated with regorafenib use or prohibited foods while on regorafenib. All patients must have a plan to be treated with dose-escalation of regorafenib based on the reDOS study. The reDOS study uses this regimen: 80mg daily for week 1, 120mg daily for week 2, 160mg daily for week 3, hold drug for week 4, and then 160mg daily for each subsequent cycle with escalation and maintenance based on tolerability. All regorafenib dose adjustments are made at the discretion of the treating medical oncology team. This study team will not make any regorafenib recommendations. Treatment with tazarotene 0.1% gel or placebo is continued daily during the week that regorafenib is held.

Outcomes will be assessed by a dermatology provider at 2-week intervals until 8 weeks, then again at week 12,

16, 20, and 24. If HFSR develops, with evidence of inflammation, patients will be treated at the discretion of the treating physician in both arms of the study.

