5.4 General Concomitant Medication and Supportive Care Guidelines

Concomitant use of systemic retinoids, treatment dose steroids or topical steroids for HFSR prior to the development of symptoms is prohibited. Other systemic agents for the treatment of HFSR are prohibited. Topical agents beyond that outlined as best practice standards (“BPS”) are prohibited.

Because there is a potential for interaction of Tazarotene with other concomitantly administered drugs through the cytochrome P450 system, the case report form must capture the concurrent use of all other drugs, over-the-counter medications, or alternative therapies. The Overall PI should be alerted if the participant is taking any agent known to affect or with the potential to affect selected CYP450 isoenzymes. Appendix C presents guidelines for identifying medications/substances that could potentially interact with the study agent(s).

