
a: Tazarotene or placebo dispensation. Tazarotene will be dispensed at the pre-study visit. Tazarotene dosing starts on Day 1 along with the first dose of regorafenib. Day 1 regorafenib and tazarotene/placebo dosing could possibly occur on the same day as the pre-study visit, after the patient has been registered and randomized; this would not be considered a protocol deviation. The starting dose of regorafenib is what is considered Day 1 and all other timepoints are based on that. There is no required order for the Day 1 regorafenib and tazarotene/placebo doses. It is preferred that the patients begin their tazarotene/placebo dose on the same day as their start of regorafenib dose (on Day 1). If however for whatever reason patients begin their tazarotene/placebo dose +/- 96 hours (4 days) from their first regorafenib dose, this will not be considered a protocol deviation, but will be noted in the data.
 
b: Epidemiology questionnaire should be completed once at screening. All other questionnaires should be collected at the indicated timepoints. These may be collected in either paper or electronic formats.
 
c: Serum pregnancy test (women of childbearing potential ONLY).
 
d: Optional skin biopsies will be obtained from a cohort of 6 patients in each arm (first 6 patients in each arm that consent to these optional biopsies)
 
e: Randomization occurs after all screening assessments have been completed and the patient's eligibility has been confirmed. This could be the same day as the screening visit or anytime up to and including Day 1. ODO will send the randomization to the research pharmacy.
 
f: Off-study treatment evaluation. This will occur 28 days +/- 7 days after the last regorafenib and tazarotene/placebo.
											

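### Exclusion 3.2.2 exempts every eligible patient already taking regorafenib with another TKI, which contradicts the monotherapy population in section 1.1

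*Combined protocol and SAP*

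**What the plan says.** Section 1.1 states the aim as a comparison "for the prevention of grade-2 or greater HFSR in patients treated with regorafenib monotherapy".

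Inclusion 3.1.1 admits patients "with a plan to initiate regorafenib, or having started regorafenib in the last 96 hours". Anyone who started earlier than that is not eligible.

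Exclusion 3.2.2 reads "Regorafenib use in combination with another TKI (unless regorafenib was started in the last 96 hours".

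The same window appears in two other places, each time as an allowance on start timing. Section 5 lets a patient take regorafenib before consenting "as long as regorafenib was started less than 96 hours from first application of tazarotene". Footnote a of the study calendar (section 10) covers the case "If however for whatever reason patients begin their tazarotene/placebo dose +/- 96 hours (4 days) from their first regorafenib dose" and says that this is not a deviation. Neither mentions a second TKI.

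On other medication, section 5 says "The study team will not be making any recommendations for dose, timing of dose, concomitant medications associated with regorafenib use", and section 5.4 says "the case report form must capture the concurrent use of all other drugs".

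**The concern.** An exclusion criterion should remove patients whom the inclusion criteria would let in. Here the exception in 3.2.2 has the same limit as the inclusion window in 3.1.1, so for patients already on both drugs the exclusion appears to do nothing. A patient on two TKIs could satisfy section 3 in full and still lie outside the population in section 1.1.

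This bears on the primary endpoint. Section 2.1 reports HFSR with other TKIs as well (34% on sorafenib and 19% on sunitinib, all grades), so a second TKI is another possible source of the event being counted. There are no stratification factors (13.3) and the primary analysis is by intention to treat (13.6.2), so any such patient stays in the main comparison. At stake are whether eligibility decisions are consistent and whether the enrolled population matches the stated one. Bias between arms is not at issue, because randomisation balances baseline use of a second TKI in expectation.

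**Working it through.** **Step 1. Apply 3.1.1 and 3.2.2 to a patient with a second TKI.**

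| Regorafenib status | Meets 3.1.1? | Excluded by 3.2.2? | Eligible? | Does 3.2.2 change the outcome? |
|---|---|---|---|---|
| Started within 96 hours | Yes | No (exception applies) | Yes | No |
| Started more than 96 hours ago | No | Yes | No | No (3.1.1 already rules the patient out) |
| Planned, not started; use means current use only | Yes | No | Yes | No |
| Planned, not started; use includes planned use | Yes | Yes | No | Yes |

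For patients already on the combination (first two rows), 3.2.2 never alters eligibility. It has force only in the last row. On that reading the same combination is barred before the first regorafenib dose and allowed for the 96 hours after it. The documents give no reason for this.

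**Step 2. Look for another rule that closes the gap.** Exclusions 3.2.9 to 3.2.11 concern active skin disease of the hands or feet, unresolved toxicity there from earlier therapy, and other investigational agents for HFSR. Section 5.4 restricts retinoids, steroids, additional topical agents and systemic agents given for HFSR. Section 5 makes no recommendation on medication taken with regorafenib. None of these bars a second TKI given for the cancer.

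**Step 3. Illustrate the size.** The documents do not say how many such patients to expect, so this step rests on assumptions.

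*Inputs from section 13.2:* 35 per arm, 50% against 25%, one-sided level 0.10, stated power 80%.

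*Assumptions:* k = 1, 2 or 4 patients per arm on a second TKI, with a 70% risk of the endpoint on placebo. The interim look is ignored.

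*Reproducing the plan's figure:* the normal approximation gives 0.818. Exact binomial enumeration, rejecting when the pooled chi-squared Z ≤ −1.2816, gives 0.809. Both agree with the stated 80%.

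*Formula:* with f = k/35, each arm's rate is (1 − f) × base rate + f × rate in co-TKI patients. For k = 4, f = 0.114:
- Placebo: 0.886 × 0.50 + 0.114 × 0.70 = 0.523.
- Tazarotene, no benefit in these patients: 0.886 × 0.25 + 0.114 × 0.70 = 0.301.

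| Effect in co-TKI patients | k = 1 (2.9%) | k = 2 (5.7%) | k = 4 (11.4%) |
|---|---|---|---|
| None (70% vs 70%) | 78.7% | 76.4% | 71.8% |
| Same 25-point benefit (70% vs 45%) | 80.7% | 80.4% | 80.1% |
| Risk halved (70% vs 35%) | 81.4% | 81.9% | 83.0% |

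With no benefit but an unchanged placebo risk of 50%, power is 78.9%, 76.9% and 72.5%. Any loss therefore comes mainly from the no-benefit assumption and hardly from the higher risk. With equal rates in both arms, anywhere from 0.500 to 0.523, the type I error is 9.4%.

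**The case against.** The strongest reply concerns weight. Monotherapy is mentioned only in section 1.1, which is a design summary and not an eligibility criterion; the primary objective, treatment plan and statistical section do not repeat it. Eligibility is confirmed by an investigator and the checklist is reviewed centrally before randomisation (4.1), which makes discordant decisions less likely. Nothing shows that a patient on regorafenib plus another TKI would ever be referred. Section 5 expects invitation when regorafenib is consented to, so many patients will not have started, and there 3.2.2 may still work. The power figures rest on invented inputs and their direction is not fixed. The plan's own uncertainty about the control rate matters far more: the same calculation at 40% against 25% gives 52% power.

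Much of this stands. The number is probably small, the power table is only an illustration, and the drafting slip is an inference. The textual point survives. The checklist is not in the documents, and one that follows section 3 would pass such a patient; central review would then confirm the error. Section 4.1 adds that recruitment depends entirely on referrals from other disease centers and that screening and randomisation may fall on the same day, which leaves little time to settle an ambiguity.

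**Conclusion.** The concern holds. As written, 3.2.2 excludes no patient already taking regorafenib with another TKI, and section 3 admits patients outside the population in section 1.1. This follows from the text alone. That the parenthesis was attached to the wrong criterion is likely but not certain.

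The consequence is an unclear population and possible dilution of the treatment difference, with no systematic bias between arms and no inflation of type I error. Its size cannot be derived from the documents. Under the assumptions above, one or two such patients per arm change power by at most about 4.5 points (80.9% to 76.4%), and by much less if they benefit from tazarotene. Two features limit the harm: 3.2.9 bars visible active disease of the hands or feet, and the case report form records concurrent drugs, so these patients can be identified. It should be corrected because it sits in a rule that decides enrolment and costs almost nothing to put right.

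**What to change.** Reconcile sections 1.1, 3.1.1 and 3.2.2, and make the eligibility checklist match. Which population is meant is for the sponsor to state.

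- **If monotherapy is intended:** delete the parenthesis from 3.2.2 and keep the 96-hour window in 3.1.1 and the start-timing passages. State whether use includes planned use. Cost: a one-line amendment and at most a few fewer eligible patients.
- **If the exception is intended:** amend 1.1 to describe the wider population, and pre-specify a sensitivity analysis of the primary endpoint that leaves out patients on another TKI, identified from the data required by 5.4. Cost: one wording change and one extra analysis, with no new data collection. With only a few such patients the analysis would say little about them, but it would show whether the main result depends on them.

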4. REGISTRATION AND RANDOMIZATION PROCEDURES

4.1 General Guidelines for DF/HCC Institutions

Institutions will register eligible participants in the Clinical Trials Management System (CTMS) OnCore. Registrations must occur prior to the initiation of any protocol-specific therapy or intervention. Any participant not registered to the protocol before protocol-specific therapy or intervention begins will be considered ineligible and registration will be denied.

An investigator will confirm eligibility criteria and a member of the study team will complete the protocol-specific eligibility checklist.

Regorafenib is not a drug that is prescribed by the Cutaneous Oncology team. This study's recruitment relies entirely on receiving referrals from other disease centers. Due to the fact that patients are referred from these outside disease centers (such as Sarcoma and GI) and that regorafenib may require insurance clearance and then mailing, we expect that screening and randomization may occur on the same day.

In an effort to increase accrual and more quickly identify potential participants that have been prescribed regorafenib in other departments within the Institute, COC will be utilizing an EPIC report to assist in the recruitment of participants. This report has been built in collaboration with pharmacy to identify patients that have been prescribed regorafenib within the last 7 days. This report can be run by the study team at any time. The COC study team may reach out to the prescribing physician to ask their permission to contact their patient directly to describe this research study and see if they would be interested in participating in this study.

The eligibility checklist(s) and all pages of the consent form(s) will be faxed to the ODQ at [contact]. The ODQ will (a) review the eligibility checklist, (b) register the participant on the protocol, and (c) randomize the participant. ODQ will send the randomization to the research pharmacy.

Randomization can only occur during ODQ business hours (8:30am - 5pm Eastern Time, Monday through Friday excluding holidays).

An email confirmation of the registration and/or randomization will be sent to the Overall PI, study coordinator(s) from the Lead Site, treating investigator and registering person immediately following the registration and/or randomization.

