10. STUDY CALENDAR

Baseline evaluations are to be conducted within 1 month prior to start of protocol therapy. Assessments must be performed prior to administration of any study agent. Study assessments and agents should be administered within \pm 3 days of the protocol-specified date, unless otherwise noted.

	Pre-Study	Cycle 1			Cycle 2		Cycle 3	Cycle 4	Cycle 5	Cycle 6	Off Study ^f
		Day 1 (Wk 0)	Day 15 (Wk 2)	Day 28 (Wk 4)	Day 42 (Wk 6)	Day 56 (Wk 8)	Day 84 (Wk 12)	Day 112 (Wk 16)	Day 140 (Wk 20)	Day 168 (Wk 24)	
		-28 days		+/-3 days	+/-3 days	+/-3 days	+/-3 days	+/-7 days	+/-7 days	+/-7 days	28 days +/- 7
First dose of Regorafenib		X									
First dose of Tazarotene		X (no more than +/- 96 hours from first Regorafenib dose)									
Study Drug Dispensation: Tazarotene or placebo^a	X			X		X	X	X	X	X	
Study Drug Accountability: Tazarotene or placebo				X		X	X				
Informed consent	X										
Demographics	X										
Medical history	X										
Concurrent meds	X	X-----X									
Physical exam	X		X	X	X	X	X	X	X	X	
Performance status	X										X
Questionnaires: HFS-14, Epidemiology Questionnaire, DLQI, Skindex16, Perceived Stress Scale Assessments ^b	X		X	X	X	X	X	X	X	X	
Adverse event evaluation		X-----X									X
B-HCG ^c	X										
Other optional correlative skin biopsies ^d	X			X (+/- 2 wk)							
ODO Randomization^e	X										

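### For a gel the protocol treats as category X, the only scheduled pregnancy test may fall up to 28 days before first application, and none is scheduled during up to 24 weeks of treatment

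*Combined protocol and SAP*

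**What the plan says.** **Hazard.** Section 3.2.3 gives the reason for the exclusion: "Pregnant women are excluded from this study because tazarotene is category X with the potential for teratogenic or abortifacient effects". Section 3.1.5 also describes tazarotene as a known teratogen, and adds that the topical dose needed to harm a human fetus is not known.

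**Test at entry.** Under 3.1.6, women of child-bearing potential "must have a negative serum pregnancy test". No time limit is attached. Section 10 says "Baseline evaluations are to be conducted within 1 month prior to start of protocol therapy", and the pre-study column is headed -28 days. The B-HCG row carries a single mark, in that column. Footnote c limits the test to women of child-bearing potential and adds no repeat.

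**Supply and duration.** Calendar footnote a says "Tazarotene will be dispensed at the pre-study visit". Further dispensing is marked at weeks 4, 8, 12, 16, 20 and 24. Section 5.5 allows treatment for up to 24 weeks.

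**Other safeguards.** Section 3.2.3 excludes women who do not comply with contraception from 4 weeks before treatment, through treatment, to at least three ovulatory cycles afterwards. Section 3.1.5 requires contraception throughout participation. It also says that if a woman becomes pregnant or suspects it, "she should inform her treating physician immediately".

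**Stopping.** Section 5.5 has six criteria. None names pregnancy. The last covers changes in the participant's condition that, in the treating investigator's judgment, make further treatment unacceptable. The dose table in Section 6 deals with skin irritation only, and Section 7 has no reporting rule for pregnancy.

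**The concern.** The exclusion is absolute at entry because of possible fetal harm, but objective verification of it happens once and can be four weeks old when the gel is first applied. A woman who conceives after the test, or too shortly before it to be detected, can start the gel and continue nightly application until she notices. Following the calendar exactly permits this.

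Two other provisions make the silence stand out. Section 5.2.2 makes continuation the default for as long as the regorafenib plan has not been permanently abandoned. Section 5.3 has a specific precaution for a pregnant caregiver who handles the gel, but no section gives a matching rule for a participant who becomes pregnant while using it.

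What is at stake is avoidable fetal exposure in women of child-bearing potential, not the validity of the trial's comparison.

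**Working it through.** The plan states no figure to reproduce. The check is a reading of every place where pregnancy, testing or stopping could appear, plus a count of days.

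**Inputs from the protocol**
- Pre-study window: 28 days by the calendar header, or about 31 days if 1 month is read literally (Section 10).
- Shortest gap from test to first dose: 0 days, because footnote a allows Day 1 dosing on the day of the pre-study visit.
- Treatment: up to 24 weeks (5.5), in 28-day cycles (Section 5).
- Maximum enrolment: 70 (13.2).

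**Tests scheduled**
- Pre-study: 1.
- Day 1: 0. Weeks 2 to 24: 0. Off study: 0.

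The calendar table is imperfectly reproduced in the text available. However, the single B-HCG mark sits in the same position as the marks for consent and demographics, and neither footnote c nor 3.1.6 mentions a repeat.

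**Intervals**
- Test to first application: 0 to 28 days.
- Treatment with no scheduled test: 6 x 28 = 168 days.
- Longest time from the only test to the end of treatment: 28 + 168 = 196 days (28 weeks).
- Dispensing visits after the pre-study visit: 6, with a test at none of them. The last is at week 24, when treatment is due to end.

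**Stopping rules that name pregnancy**
- Section 5.5: 0 of 6 criteria. Section 6: none.

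**Effect of a shorter window**
- Moving the latest permitted test from day -28 to day -7 removes 28 - 7 = 21 days from the maximum gap.
- As an illustration, assume a test turns positive 7 to 14 days after conception (an assumption; the protocol gives no such figure). A day -28 test then cannot exclude conceptions in the last 28 + 7 = 35 to 28 + 14 = 42 days before the first dose. A day -7 test leaves 7 + 7 = 14 to 7 + 14 = 21 days.
- With 4-weekly tests as well, the longest nominal interval without a test is 7 + 28 = 35 days, against 196 now.

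**The case against.** The strongest reply is that the plan does maintain the exclusion after entry. Contraception is required before, during and after treatment, and the 4 weeks required beforehand cover the whole 28-day screening gap. That stands. A reader might infer that nothing protects the participant once she is enrolled, and the documents do not support that. What is missing is a scheduled means of detecting contraceptive failure.

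A reader might also infer that a pregnant participant could not be taken off the gel, or that nothing would prompt it. That goes too far. The last item of 5.5 gives the investigator a route, 5.5 says participants will be removed when any criterion applies, and the protocol's own description of the drug supplies the reason. The accurate statement is that pregnancy is not named and the decision is left to judgment.

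Three further inferences should be resisted.

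- **Delay before the first dose.** Section 4.1 notes that "regorafenib may require insurance clearance and then mailing". This might be read as evidence of long gaps between test and first dose. The sentence gives it as a reason to expect screening and randomization on the same day. Some patients may also enter after starting regorafenib, with the gel due within 96 hours of that start. The 28-day gap is permitted, but its frequency is unknown.
- **Who is told.** Section 4.1 also says "Regorafenib is not a drug that is prescribed by the Cutaneous Oncology team", so one might suppose that a woman's report would go to someone with no control of the gel. The protocol does not define the treating physician. However, it generally calls the regorafenib prescribers the treating medical oncology team, and it uses treating physician when describing on-study management of the skin reaction. The inference is conjecture.
- **Probability of pregnancy.** The documents give neither the share of women of child-bearing potential nor a contraceptive failure rate. Any probability would rest on outside assumptions, so none is offered.

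Consent pages were not available and may add instructions. The calendar and 5.5, where a repeat test or a named stop would be expected, were available.

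**Conclusion.** The point holds as a correctable participant-safety gap. There is one test, up to 28 days before first application, and no scheduled test over up to 168 days of treatment with a drug the protocol treats as category X. Contraceptive failure would come to light only through self-report, and 5.5 permits stopping without naming pregnancy. The counts come directly from the calendar, 3.1.6 and 5.5. The 196-day figure is a maximum: it applies to a woman tested at day -28 who completes 24 weeks, not to the typical participant.

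The test timing and the lack of on-treatment tests are the substance. Naming pregnancy in 5.5 is a supporting clarification. The actual risk is not quantified and may be small. The case for change rests on the protocol's own view of the hazard and on the low cost. Sample size, power, the primary endpoint and its analysis are unaffected.

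**What to change.** 1. In 3.1.6 and the calendar, require the negative serum test within a short window before the first gel application, and repeat it if Day 1 falls later. Seven days is a suggested value; it does not come from the documents.
2. Add a urine test for women of child-bearing potential, in both arms, at the existing 4-weekly visits (weeks 4 to 24), before any new tube is dispensed.
3. In 5.5, list pregnancy as a mandatory immediate stop. In 3.1.5 and Section 7, require that the study team and the Overall PI be told.

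**Cost.** An occasional repeat test before a delayed start, up to 6 urine tests per woman at visits that already take place, and amended protocol and consent wording. If 5% to 20% of the maximum 70 participants are women of child-bearing potential (an assumption), the urine tests number 70 x 0.05 x 6 = 21 to 70 x 0.20 x 6 = 84. There would be fewer if enrolment stops at the interim look or participants leave treatment early. The urine tests need no added visit, and the analysis does not change.
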